4.3. Part 2: Disease-Specific Expansion Cohort(s)

Once the RP2D has been determined, subjects will be enrolled in disease-specific expansion cohorts at the RP2D in order to better characterize the clinical activity and safety profile of GSK3326595. Expansion cohorts will enroll subjects with TNBC, mTCC, recurrent GBM, NHL (all subtypes recruited to Protocol Amendments 1-4 and indolent subtypes of NHL recruited to Protocol Amendment 5 onwards, which will be analyzed based on TP53 status: p53 mutant and p53 wild-type), ACC (which will be separated into two separate cohorts: one dosed with GSK3326595 capsules, and a second dosed with GSK3326595 tablets [this tablet cohort will enroll subjects who have not received any systemic therapy for their locally advanced or metastatic ACC]), ER+BC, HPV-positive solid tumors of any histology, and p53 wild-type NSCLC of any histological subtype. Other tumor types may be added via protocol amendment, based on additional pre-clinical data and/or clinical responses observed during Part 1 or Part 2 of the study.

Subjects in Part 2 will start with a continuous daily dosing schedule unless safety, PK or PD data necessitate a different dosing schedule. The final dose and regimen for Part 2 will be decided upon completion of dose escalation in Part 1. Dose reduction and/or scheduled interruptions will be permitted based on tolerability and toxicity.

Plasma samples for PK evaluation will be collected, at reduced frequency compared to Part 1, in all subjects. Plasma samples and other clinical samples (e.g. lymph node or bone marrow biopsies) will be collected pre- and post- study drug treatment as defined in the Time and Events Table in Section 8.1 for the PD evaluations. The timing of samples may be altered and/or extra samples may be obtained at additional time points to ensure thorough PK and PD monitoring. For example, the timing of PK and PD monitoring may be moved earlier or later in the evaluation schedule based on emerging preclinical or clinical data that suggests a more optimal time frame to monitor biologic activity.

4.3.1. Type and Number of Subjects (Part 2)

It is estimated that up to 316 subjects will be enrolled in the disease-specific expansion cohorts of the study. Cohorts will initially be limited to the following diseases (see Section 5.1 for all required disease characteristics); however, additional tumor-specific cohort(s) may be added based upon emerging pre-clinical and clinical data from Part 1 or Part 2 of the study:

- Triple-negative breast cancer (TNBC)
- Metastatic transitional cell carcinoma of the urinary system (mTCC)
- Glioblastoma multiforme (GBM)
- Non-Hodgkin's lymphoma (NHL) all subtypes recruited to Protocol Amendments 1-4 and indolent subtypes of NHL recruited to Protocol Amendment 5 onwards, without mutations in the TP53 gene (p53 wild-type, NHL[-])
- Non-Hodgkin's lymphoma all subtypes recruited to Protocol Amendments 1-4 and indolent subtypes of NHL recruited to Protocol Amendment 5 onwards, with mutations in the TP53 gene (p53 mutant, NHL[+])
- Adenoid cystic carcinoma (ACC), dosed with GSK3326595 capsule formulation
- Adenoid cystic carcinoma (ACC), dosed with GSK3326595 tablet formulation, in a population that is systemic therapy-naïve.
- Hormone receptor-positive adenocarcinoma of the breast (ER+BC)
- Human papillomavirus (HPV)-positive solid tumors of any histology
- p53 wild-type non-small cell lung cancer (NSCLC) of any histological subtype

In Part 2, subjects will not be replaced if they prematurely discontinue therapy.

Initially, the NHL cohorts enrolled subjects irrespective of histological subtype. However, in December 2019 it was noted that of the subjects enrolled with high-grade and other aggressive subtypes of diffuse large B-cell lymphoma (DLBCL), including double- and triple-hit lymphomas, there were zero objective responses out of 14 subjects dosed. Conversely, clinical benefit was observed in subjects with more indolent subtypes (including complete/partial responses in were observed in subjects with FL and transformed follicular lymphoma (tFL), and stable disease for several disease assessments was observed in subjects with MCL). Therefore, Protocol Amendment 5 limited further enrollment to this population to subjects with more indolent disease who may receive more benefit from treatment with GSK3326595 monotherapy.

4.3.2. R2PD Dose Selection

Subjects will start dosing on Day 1 with the dose and schedule selected as the RP2D in Part 1 of the study.

At a 21 March 2018 investigator meeting, 400 mg once daily (QD) was selected as the RP2D, based on safety, tolerability, efficacy, PK, and PD. Dose reductions and scheduled interruptions are permitted for toxicity and tolerability as described in Table 3. At that meeting, it was also determined that if emerging data demonstrated that 400 mg QD proved intolerable for a majority of subjects, that the starting dose for all subjects enrolled from that time forward may be reduced (e.g., to Dose level [DL]-1). The final dose selection will take into account all available clinical data, as well as a PK/PD model to predict the optimal dose with minimal cytopenias.

RP2D	400 mg QD
DL-1	300 mg QD
DL-2	200 mg QD
DL-3	200 mg QD, administered for 3 weeks, followed by a 1-week rest period

Table 3RP2D and Planned Dose Reduction

Note: These dose levels may be adjusted on a case-by-case basis after discussion with the GSK medical monitor.

Subsequent evaluation of safety and tolerability data was performed, using data from the 04 February 2019 data cut included in the IB for GSK3326595 [GlaxoSmithKline Document Number 2017N314773_03]. As of that date, 71 subjects had been treated at the 400 mg RP2D in the 204653 study. Of those 71 subjects, 33 (46%) required at least one dose reduction. Of the 33 subjects requiring dose reduction, the majority (23 subjects [70%]) remained on 300 mg for their duration on study. Overall, only 10 subjects (14% of the total number treated at 400 mg) required more than one dose reduction (i.e., to doses below 300 mg).

Clinical activity was observed in Part 1, in subjects with ACC who were treated at doses of 300 mg and below. Of the three patients who exhibited confirmed partial responses, two were started at a dose of 200 mg QD and remained at that dose throughout their time on study. The third responder began treatment with GSK3326595 at 400 mg QD, but dose reduced to 300 mg QD after the first month on treatment.

All new subjects enrolled, following approval of Protocol Amendment 4 (food effect and relative bioavailability sub-study in Part 1, and all dose expansion cohorts in Part 2), will start on 300 mg QD (i.e., at Dose level-1 [DL-1] in Table 3). In all cohorts, dose reduction for toxicity will be permitted, as described in Table 3.

4.3.3. Statistical Design

Continued recruitment into each disease-specific expansion cohort is determined using the rules described in this section.

4.3.3.1. GBM Cohort

In Part 2, the GBM cohort will employ a Bayesian adaptive design that allows the study to be frequently monitored with the constraint of both Type I and Type II error rates. The first interim analysis will be conducted after a minimum of 10 evaluable subjects who have had at least three post-baseline assessments, have progressed or died, or have permanently discontinued from study treatment. Up to 28 subjects may be enrolled in the GBM cohort; for details of the design and decision rules, refer to Section 11.3.

4.3.3.2. mTCC, TNBC, and NHL Cohorts

For mTCC, TNBC and NHL cohorts, a "basket" Bayesian hierarchical modeling design that allows the trial to be frequently monitored with the constraint of both Type I and Type II error rates will be used. Clinical response will be defined as ORR, per standard evaluation criteria (see Section 14.4 for definitions of response assessments and criteria). Bayesian hierarchical modeling will be used to investigate the clinical activity of GSK3326595 in the four tumor-specific cohorts of subjects. Hierarchical modeling allows information about the treatment effect in one cohort to be 'borrowed' when estimating the treatment effect in another cohort [Berry, 2013].

Clinical activity will be monitored through frequent interim analyses. The first interim analysis will be conducted when about 40 evaluable subjects are enrolled across the four tumor-specific cohorts (mTCC, TNBC, p53 WT NHL, and p53 mutant NHL) at a dose level based on RP2D or at least 10 evaluable subjects are available in any cohort. Subjects treated at the RP2D in Part 1, with disease subtypes under study in Part 2, will be incorporated into clinical activity analysis provided that they are evaluable. Each subsequent interim analysis can be conducted after every five additional subjects become evaluable. The timing of subsequent interim analyses will be based on the enrollment rate into each of the cohorts with the expected duration of Part 2 of the trial to be 104 weeks. A subject is evaluable for the interim futility analysis if they have either progressed or died, withdrawn from the study treatment, or are ongoing and have completed at least two post baseline disease assessments.

Decisions are based on whether the posterior probability that the ORR exceeds its corresponding historical control is sufficiently low compared to fixed statistical thresholds. If this posterior probability is sufficiently low within a given cohort (≤ 0.15), then enrollment may be halted early for futility. At the final analysis and after the study has been closed, if the posterior probability is sufficiently high (≥ 0.87), then the dose will be declared efficacious for that cohort. Separate from model estimates, the observed ORR will also be reported for each cohort.

Enrollment into each disease-specific cohort will continue during the conduct of each interim analysis subsequent to the decision of whether or not to declare futility. The total number may be increased up to a total of 32 evaluable subjects for the TNBC cohort, up to a total of 25 evaluable subjects for each of the two NHL cohorts, and up to 40 evaluable subjects for the mTCC cohort, depending on the results observed; a separate decision will be made for each disease cohort. Enrollment into each tumor specific cohorts can only be terminated for futility (i.e., lack of clinical activity), notwithstanding the provisions of Section 5.5; otherwise enrollment will continue to the planned maximum sample size in each cohort. Inference stemming from the Bayesian hierarchical model of GSK3326595 efficacy in subjects harboring these four tumor types are intended to inform decision making. Actual decisions will depend on the totality of the data.

Subjects enrolled in Part 1 may be included in the Part 2 efficacy analysis provided that they were treated at the RP2D and have a disease under study in Part 2.

The decision to terminate a disease-specific cohort will not depend solely on the results of the statistical model but will take all factors into account, including the results of the model, safety, tolerability, PK, and PD data. In some cases (e.g., under-representation of a given predictive biomarker in the subjects treated at the time of interim analysis), additional subjects in a cohort may be enrolled even if the model suggests a low likelihood of activity in that tumor type.

4.3.3.3. ACC Cohorts (Capsule and Tablet Formulation)

The Simon's optimal two stage design will be utilized for the ACC cohorts. Up to 38 subjects in the capsule cohort will be enrolled, and up to 50 subjects in the tablet cohort will be enrolled. One interim analysis will be performed in each cohort after at least the first 10 treated subjects for the capsule cohort and the first 17 treated subjects for the tablet cohort become evaluable (i.e. who have had at least three post-baseline assessments, have progressed or died, or have permanently discontinued from study treatment). Please refer to Section 11.5 for details of the design and decision rules.

4.3.3.4. Hormone Receptor-Positive Breast Cancer Cohort

The ER+BC cohort will employ a Bayesian adaptive design that allows the study to be frequently monitored with the constraint of both Type I and Type II error rates. The first interim futility analysis will be conducted after a minimum of 10 evaluable subjects who

have had at least two post-baseline assessments, have progressed or died, or have permanently discontinued from study treatment. If the cohort does not meet the futility criteria, then up to 25 additional subjects may be enrolled in this cohort; for details of the design and decision rules, refer to Section 11.6.

4.3.3.5. HPV-Positive Solid Tumor Cohort

The HPV-positive cohort will employ a Bayesian adaptive design that allows the study to be frequently monitored with the constraint of both Type I and Type II error rates. The first interim futility analysis will be conducted after a minimum of 10 evaluable subjects who have had at least two post-baseline assessments, have progressed or died, or have permanently discontinued from study treatment. If the cohort does not meet the futility criteria, then up to 18 additional subjects may be enrolled in this cohort; for details of the design and decision rules, refer to Section 11.7.

4.3.3.6. NSCLC Cohort

The p53 wild-type NSCLC cohort will be used to estimate the clinical activity for GSK3326595 for this population. The analysis will be performed on a minimum of 10 and maximum of 15 evaluable subjects with confirmed p53 wild-type status. The additional 5 subjects are intended to account for any discrepancies between local p53 testing and central, comprehensive testing to ensure a minimum of 10 evaluable p53 wild-type subjects. Only those evaluable subjects whose central test results confirm p53 wild-type status will be included in the analysis. A subject is evaluable for analysis if they have either progressed or died, withdrawn from the study treatment, or are ongoing and have completed at least two post-baseline disease assessments. A Simon's optimal two stage design will be utilized as a framework for the analysis of this cohort, where one interim analysis will be performed after at least the first 10 treated subjects become evaluable. Please refer to Section 11.5 for details of the design and decision rules.

4.4. Part 3: GSK3326595 + Pembrolizumab Combination Study [Active in all regions, except France]

The primary objective of Part 3 is to evaluate the safety and tolerability of GSK3326595 when administered in combination with pembrolizumab in subjects with select solid tumors. As described in Section 4.4.4, three cohorts will be evaluated. All subjects will receive pembrolizumab at the approved dose (200 mg IV every 3 weeks [q3w]), in combination with GSK3326595 dosed orally at 100 mg QD, 200 mg QD, or 300 mg QD.

All available data from Part 3, including safety, tolerability, efficacy, PK, and PD will be used to select a dose of GSK3326595 to be administered with pembrolizumab in future studies. In order to collect PD data, pre- and on-study biopsies will be required for all subjects. Subjects will receive GSK3326595 at the assigned dose as monotherapy for 14 days, at which time the on-study biopsy will be collected. Subjects will then commence therapy with pembrolizumab administered every 3 weeks. Safety will be

assessed continuously. Cohort(s) may be closed to further enrolment based on toxicity emerging at any time on study, as described in Section 4.4.4.

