- HPV-positive solid tumor of any primary histology NOTE: HPV-positive status may be determined locally via any generally accepted test [e.g., HPV DNA OR p16 immunohistochemistry]. A minimum of 10 subjects must be enrolled with cervical cancer;
- non-Hodgkin's lymphoma that is NOT one of the following subtypes, as determined by local laboratory testing:
 - Burkitt's lymphoma or other high-grade lymphoma
 - Double- or triple-hit large B-cell lymphoma NOTE: Any questions regarding eligibility of subtypes should be directed to the medical monitor
- OR NSCLC, of any histologic sub-type; with local mutational analysis demonstrating wild-type status of TP53 (i.e., p53 wild-type NSCLC)
 NOTE: Subjects in the cohort must have previously received treatment with an anti-PD1 and/or PD-L1 therapy or be considered ineligible to receive therapy with these agents
 NOTE: Subjects where twees twees herbor actionable mutations (a.g., EGEP)

NOTE: Subjects whose tumors harbor actionable mutations (e.g., EGFR mutations or ALK rearrangements) must have received prior therapy with targeted agents prior to enrollment.

- c. Part 3: Histologically- or cytologically-confirmed diagnosis of metastatic or nonresectable NSCLC (of any histologic sub-type), mTCC, HNSCC, or melanoma that failed to respond to prior treatment with PD-1 or PD-L1 targeted therapy and recurrent/metastatic cervical squamous cell carcinoma that have progressed on or after PD-1 or PD-L1 directed therapy or are PD-1/PD-L1 treatment naïve.
- NOTE: NSCLC, mTCC, HNSCC or Melanoma Subjects must have had SD (with subsequent documented progression as per iRECIST) or PD as best response to prior PD-1 or PD-L1 targeted therapy to be eligible for enrollment.
- 6. Prior therapy
 - ACC tablet cohort: subjects must be systemic therapy-naïve. Prior surgery and/or radiation is permitted
 - NHL cohort: subjects may have received up to 4 prior lines of systemic therapy for disease
 - Tumors with actionable mutations (e.g., BRAF V600E in melanoma; EGFR mutations or ALK rearrangements in NSCLC) must have received prior therapy with targeted agents prior to enrollment
 - Apart from ACC tablet cohort, subjects must have received at least one line of prior systemic therapy (or have a disease for which no approved therapy exists), AND have no standard-of-care therapy that would be expected to achieve a durable clinical response, OR refuse standard therapy, OR are not candidates for standard therapy.
- 7. Evaluable disease

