11.8. Statistical Design for NSCLC cohort

The Part 2 NSCLC cohort is intended to explore the clinical activity in the p53 wild-type NSCLC population. Simon's optimal two-stage design (Simon, 1989) will be used as a basis for analysis of the NSCLC cohort. The null hypothesis that the true response rate is 10% will be tested against a one-sided alternative. ORR will be assessed for the 10 subjects that are confirmed with p53 wild-type.

In the first stage, 10 subjects will be accrued. If there are 1 or fewer responders in the first 10 subjects, the cohort will be stopped for futility. If 2 or more responses are observed, further expansion of the p53 wild-type NSCLC cohort may be triggered via protocol amendment or as a part of another study. If the cohort were to expand to 29 subjects, the null hypothesis would be rejected if 6 or more responders are observed. This design yields a type I error rate of 0.047 and power of 80.5% when the true response rate is 30%.

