3.1.7. Interim Analysis for Part 2: Statistical Design for NSCLC Cohort

The Part 2 NSCLC cohort is intended to explore the clinical activity in the p53 wild-type NSCLC population. Simon's optimal two-stage design will be used as a basis for analysis of the NSCLC cohort. The null hypothesis that the true response rate is 10% will be tested against a one-sided alternative. ORR will be assessed for the 10 subjects that are confirmed with p53 wild-type.

In the first stage, 10 subjects will be accrued. If there are 1 or fewer responders in the first 10 subjects, the cohort will be stopped for futility. If 2 or more responses are observed, further expansion of the p53 wild-type NSCLC cohort may be triggered via protocol amendment or as a part of another study. If the cohort were to expand to 29 subjects, the null hypothesis would be rejected if 6 or more responders are observed. This design yields a type I error rate of 0.047 and power of 80.5% when the true response rate is 30%.

Note that at the time GSK made a decision to cease enrollment in the study, this cohort did not have 10 subjects. Therefore, the interim analysis was not conducted.

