4. ANALYSIS POPULATIONS

4.1. List of Populations

Population	Definition / Criteria	Analyses Evaluated
Screened	All participants who were screened for eligibility	Study Population
Enrolled	All participants who signed the ICF	Study Population
All Treated	Defined as all subjects who receive at least one dose of GSK3326595.	Safety Anti-cancer activity Efficacy (final analysis)
All Evaluable	For Part 1: Defined as subjects who have had any post-baseline response data, or who discontinued without any response data collected. For Part 2: Defined as subjects who have had	Interim Analysis
	two post baseline disease assessments, have progressed or died, or permanently discontinued from the study treatment for mTCC, TNBC, ER+BC, HPV+, NHL and NSCLC cohorts. It is defined as subjects who have had three post baseline disease assessments, have progressed or died, or permanently discontinued from the study treatment for ACC and GBM cohorts.	

Table 7Analysis Populations

Population	Definition / Criteria	Analyses Evaluated
Pharmacokinetic (PK)	Consist of all subjects from the All Treated Population for whom a PK sample is obtained and analyzed. Note: PK samples that may be affected by protocol deviations will be reviewed by the study team to determine whether or not the sample will be excluded.	PK
Pharmacodynamic (PD)	Defined as subjects in the All Treated Subjects Population for whom paired and evaluable tumor biopsies (pre- and on- treatment time points) or plasma or urine were obtained and analyzed for biomarkers.	PD

Refer to Appendix 12: List of Data Displays which details the population used for each display. Note that for the interim analyses, the All Evaluable population will be used for efficacy analyses, and the All-Treated Population will be used for safety analyses. However, for the final analysis, the All Treated Population will be used for all displays.

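### Protocol 4.3.3.6 and 11.8 restrict the NSCLC response rate to centrally confirmed p53 wild-type subjects, but other protocol sections and the SAP use All Treated, and the SAP does not declare the difference

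*Protocol*

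**What the plan says.** **Restricted set.** Protocol 4.3.3.6 says: "Only those evaluable subjects whose central test results confirm p53 wild-type status will be included in the analysis". It caps the cohort at 15 and explains the margin above 10: "The additional 5 subjects are intended to account for any discrepancies between local p53 testing and central, comprehensive testing". Protocol 11.8 speaks of ORR in confirmed wild-type subjects. SAP 3.1.7 carries the same sentence, "ORR will be assessed for the 10 subjects that are confirmed with p53 wild-type", in its interim-analysis section, and then records that the cohort had fewer than 10 subjects when enrolment ceased and that the interim was not done.

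**Entry.** Protocol 5.1 admits NSCLC subjects "with local mutational analysis demonstrating wild-type status of TP53". A subject can therefore be treated before any central result is known.

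**Unrestricted set.** Protocol 11.9.5 evaluates anti-cancer activity on All Treated, and its evaluable definition for NSCLC has no p53 element. Protocol 11.10.1, which discusses the NSCLC cohort by name, also assigns efficacy to All Treated. SAP 4.1 states that "for the final analysis, the All Treated Population will be used for all displays". SAP Table 2.1 reports best response on All Treated by Part 2 cohort.

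**Related SAP text.** SAP 5.1.1 defines the NSCLC display groups by dose and formulation. In the same list it sets NHL p53 status from central data, with missing results classed as Unknown. SAP 5.4.2 plans no subgroups. SAP 2.1 declares no change from Amendment 8, and its list of exceptions does not mention the NSCLC analysis set.

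**The concern.** The cohort was opened to estimate activity in p53 wild-type NSCLC. The protocol foresaw that local and central tests would sometimes disagree, and it dealt with this by over-enrolling and analysing only confirmed subjects. As planned, the final table does not separate confirmed subjects from those whose central result is mutant or missing. If any such subjects exist, the reported ORR answers a different question from the one the cohort was set up to answer, and a reader of the table could not tell. In a cohort of fewer than 10, moving one subject in or out of the denominator visibly changes the percentage.

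**Working it through.** **1. The plan's own figures.** Inputs from Protocol 11.8: "The null hypothesis that the true response rate is 10% will be tested against a one-sided alternative"; "If there are 1 or fewer responders in the first 10 subjects, the cohort will be stopped for futility"; "If the cohort were to expand to 29 subjects, the null hypothesis would be rejected if 6 or more responders are observed". Stage 2 therefore adds 29 − 10 = 19 subjects. The probability of rejecting at true rate p is

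Σ (x = 2 to 10) P(X₁ = x; 10, p) × P(X₂ ≥ 6 − x; 19, p).

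- p = 0.10: 0.0471 (stated 0.047)
- p = 0.30: 0.8051 (stated 80.5%)

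Both reproduce. They depend only on the counts and the assumed rate, so the choice of analysis set for the final table does not alter them.

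**2. The sections side by side.**

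| Place | Set for NSCLC response | p53 criterion |
|---|---|---|
| Protocol 4.3.3.6 | Evaluable, centrally confirmed | Yes |
| Protocol 11.8 | Confirmed wild-type | Yes |
| Protocol 11.9.5 | All Treated | No |
| Protocol 11.10.1 | All Treated | No |
| SAP 3.1.7 (interim, not run) | Confirmed wild-type | Yes |
| SAP 4.1 and Table 2.1 (final) | All Treated | No |

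The p53 criterion matters more than evaluability here. Under Protocol 11.9.5 a subject is evaluable after two post-baseline assessments, progression, death or permanent discontinuation of treatment. By the final cut-off few treated subjects, if any, should fail that.

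**3. How much discordance the plan allowed for.** 5 of 15 = one third.

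**4. Illustrative effect on the expected ORR.** Assumptions: 9 treated, the most that SAP 3.1.7 allows if its statement refers to treated subjects; a true ORR of 30% in wild-type subjects (the target in Protocol 11.1); and q = 0 to 10% in discordant subjects, which is my assumption. With d discordant, expected All Treated ORR = [(9 − d) × 0.30 + d × q] / 9.

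- d = 1: 26.7% to 27.8%
- d = 2: 23.3% to 25.6%
- d = 3 (one third): 20.0% to 23.3%

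The confirmed set stays at 30%. If discordant subjects responded as often as wild-type subjects, there would be no dilution.

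**5. Illustrative effect on an observed ORR** (exact 95% intervals).

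- 2 responses, both confirmed: 2/9 = 22.2% (2.8% to 60.0%) against 2/6 = 33.3% (4.3% to 77.7%).
- 2 responses, both discordant: 2/9 = 22.2% against 0/6 = 0% (0% to 45.9%).
- 1 response, confirmed, with one discordant subject of 8: 1/8 = 12.5% against 1/7 = 14.3%.

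The first two cases use the full one-third discordance. The third shows how small the effect can be.

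**The case against.** The strongest reply is that the SAP follows the protocol's own population sections. Protocol 11.9.5 and 11.10.1 assign efficacy to All Treated, and Protocol 11.9.4 makes stratification of response by p53 status optional. This stands. A reader might infer that the SAP simply departs from the protocol, but the documents do not support that, because the protocol is inconsistent within itself and the SAP inherits the conflict. It does not settle the matter, because 4.3.3.6 is a rule written for this one cohort and the general sections do not say that they override it.

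A second reply is that the restriction belonged to the futility look. Protocol 11.9.6 places the wild-type condition there, and the look was never run. This stands in part. However, 4.3.3.6 describes estimation of activity in this population as the cohort's purpose, and the final ORR display remains after the interim falls away.

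Third, a reader might infer that misclassified subjects are in fact mixed into the result. The documents do not show this. They give no central p53 results for NSCLC, and there may be no discordant subject at all.

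Fourth, with so few subjects the intervals overlap almost entirely under either denominator. That is true, and it limits the importance of the point. It does not remove the need to say which subjects the estimate describes.

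**Conclusion.** The point holds as an unreconciled analysis set. Protocol 4.3.3.6 and 11.8 call for evaluable, centrally confirmed wild-type subjects. Protocol 11.9.5 and 11.10.1, SAP 4.1 and Table 2.1 call for All Treated with no p53 criterion, and SAP 2.1 does not record the difference. Any locally misclassified subjects would enter the only final NSCLC ORR.

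The size cannot be fixed from the documents. Under the stated assumptions it runs from about 2 percentage points (12.5% against 14.3%) to 11 points (22.2% against 33.3%) when all responses are in confirmed subjects. It is larger, and in the other direction, if responses fall in discordant subjects. The consequence is confined to what a small descriptive estimate means and what its denominator is. It would be wrong to read it as damage to the two-stage type I error or power, since both figures reproduce and no formal test remains in this cohort.

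**What to change.** - In SAP Table 2.1, report NSCLC ORR for evaluable subjects with centrally confirmed p53 wild-type status as the row that answers the cohort's question. Keep the All Treated row as supportive.
- Add a listing of central p53 status for each NSCLC subject, and show missing central results as Unknown, as SAP 5.1.1 does for NHL.
- Align Protocol 4.3.3.6 and 11.8 with 11.9.5 and 11.10.1, or record in SAP 2.1 which set governs the final NSCLC analysis and why.
- A matching PFS row in Table 2.6 is optional and supportive, because Protocol 11.8 and SAP 3.1.7 refer to ORR.

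The cost is one table row and one short listing, using central results that the protocol already relies on. The statistical cost is a smaller denominator and a wider interval for the confirmed set.
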